4.2.2 Nontherapy Precautions and Restrictions

4.2.2.1 Precautions

Subjects should not undergo any elective medical procedure without prior consultation with the investigator. An elective procedure (minor surgery, dental surgery, orthopedic surgery, etc.) that might require hospitalization or anesthesia should be deferred until after the trial whenever clinically appropriate.

4.2.2.2 Restrictions

Subjects will be instructed to refrain from drinking alcoholic beverages or using illicit drugs during participation in the trial. The investigator may request a urine drug screen or a blood alcohol test at any time during the trial if there is a suspicion of illicit drug or alcohol use.

5 Reporting of Adverse Events

5.1 Definitions

An AE is defined as any untoward medical occurrence in a patient or clinical trial subject administered a medicinal product and which does not necessarily have a causal

Protocol 31-14-204

relationship with this treatment. AEs would not include information recorded as medical history at screening for preplanned procedures for which the underlying condition was known and no worsening occurred. An adverse reaction is any untoward and unintended response to an IMP-related to any dose administered.

A suspected adverse reaction is any AE for which there is a reasonable possibility that the IMP caused the AE. For the purpose of Investigational New Drug (IND) safety reporting, "reasonable possibility" means there is evidence to suggest a causal relationship between the IMP and the AE. Suspected adverse reaction implies a lesser degree of certainty about causality.

An SAE includes any event that results in any of the following outcomes:

- Death
- Life-threatening; ie, the subject was, in the opinion of the investigator, at immediate risk of death from the event as it occurred. It does not include an event that, had it occurred in a more severe form, might have caused death.
- Persistent or significant incapacity/disability or substantial disruption of the ability to conduct normal life functions.
- Requires in-patient hospitalization or prolongs hospitalization.
 - Hospitalization itself should not be reported as an SAE; whenever possible the reason for the hospitalization should be reported.
 - Hospitalizations or prolonged hospitalizations for social admissions (ie, those required for reasons of convenience or other non-medical need) are not considered SAEs.
- Congenital anomaly/birth defect.
- Other medically significant events that, based upon appropriate medical judgment, may jeopardize the subject and may require medical or surgical intervention to prevent one of the outcomes listed above; eg, allergic bronchospasm requiring intensive treatment in an emergency room or home, blood dyscrasias or convulsions that do not result in hospitalization, or the development of drug dependency or drug abuse.

Nonserious AEs are all AEs that do not meet the criteria for a "serious" AE.

Immediately Reportable Event (IRE):

- Any SAE.
- Any AE related to occupational exposure.
- Potential serious hepatotoxicity (see [Section 5.4](#)).

Protocol 31-14-204

- Pregnancies are also defined as IREs. Although normal pregnancy is not an AE, it will mandate IMP discontinuation and must be reported on an IRE form to the sponsor. Pregnancy will only be documented on the AE eSource page if there is an abnormality or complication.

Clinical Laboratory Test Value Changes: It is the investigator's responsibility to review the results of all laboratory tests as they become available. This review will be documented by the investigator's dated signature on the laboratory report. For each abnormal laboratory test result, the investigator needs to ascertain if this is an abnormal (ie, clinically significant) change from baseline for that individual subject. This determination, however, does not necessarily need to be made the first time an abnormal value is observed. The investigator may repeat the laboratory test or request additional tests to verify the results of the original laboratory tests. If this laboratory value is considered medically relevant by the investigator (subject is symptomatic, requiring corrective treatment or further evaluation), or if the laboratory value leads to discontinuation, and/or fulfills a seriousness criterion, this is considered an AE.

Severity: Adverse events will be graded on a 3-point scale and reported as indicated on the eSource. The intensity of an adverse experience is defined as follows:

- 1 = Mild:** Discomfort noticed, but no disruption to daily activity.
- 2 = Moderate:** Discomfort sufficient to reduce or affect normal daily activity.
- 3 = Severe:** Inability to work or perform normal daily activity.

IMP Causality: Assessment of causal relationship of an AE to the use of the IMP is defined as follows:

- Related:** There is a reasonable possibility of a temporal and causal relationship between the IMP and the AE.
- Not Related:** There is no temporal or causal relationship between the IMP and the AE.

5.2 Eliciting and Reporting Adverse Events

The investigator will periodically assess subjects for the occurrence of AEs. To avoid bias in eliciting AEs, subjects should be asked the non-leading question: "How have you felt since your last visit?" All AEs (serious and nonserious) reported by the subject must

Protocol 31-14-204

be recorded on the source documents and eSource documentation provided by the sponsor. Serious AE collection is to begin after a subject has signed the ICF.

Use medical terminology in AE reporting. Adverse events should be reported as a single unifying diagnosis whenever possible or, in the absence of a unifying diagnosis, as individual signs or symptoms. Exacerbation or disease progression should be reported as an AE only if there are unusual or severe clinical features that were not present, or experienced earlier, or not expected based on the course of the condition.

In addition, the sponsor must be notified immediately by telephone, fax, or e-mail of any IREs according to the procedure outlined below, in [Section 5.3](#). Special attention should be paid to recording hospitalization and concomitant medications.

5.3 Immediately Reportable Events

The investigator must immediately report after either the investigator or site personnel become aware of any SAE, serious hepatotoxicity, or confirmed pregnancy, by telephone, fax, or e-mail to the sponsor using the contact information on the cover page of this protocol. An IRE form must be completed and sent by e-mail, fax, or overnight courier to the sponsor. (Please note that the IRE form is NOT the AE eSource.)

Subjects experiencing SAEs should be followed clinically until their health has returned to baseline status, or until all parameters have returned to normal or have otherwise been explained. It is expected that the investigator will provide or arrange appropriate supportive care for the subject and will provide prompt updates on the subject's status to the sponsor.

5.4 Potential Serious Hepatotoxicity

For a subject who experiences an elevation in AST or ALT that is ≥ 3 times the ULN, a total bilirubin level should also be evaluated. If the total bilirubin is ≥ 2 times the ULN, complete an IRE form with all values listed and also report as an AE on the eCRF.

5.5 Pregnancy

For purposes of this pediatric trial, FOCBP are considered all female subjects ≥ 12 years of age and all female subjects < 12 years of age, if menstruation has started.

For FOCBP and for males who are sexually active, there must be a documented agreement that the subject and/or their partner will take effective measures (eg, double-barrier method) to prevent pregnancy during the course of the trial and for 30 days after the last dose of IMP. Two of the following precautions must be used:

Protocol 31-14-204

vasectomy, tubal ligation, vaginal diaphragm with spermicide, intrauterine device, birth control pills, birth control depot injection, birth control implant, condom with spermicide, or sponge with spermicide. Any single method of birth control, including vasectomy and tubal ligation, may fail, leading to pregnancy. The contraceptive method will be documented at each trial visit. Abstinence will be permitted, if it is documented at every trial visit.

Before enrolling FOCBP in this clinical trial, investigators must review the below guidelines about trial participation with all FOCBP. The topics should generally include:

- General information
- Informed consent form
- Pregnancy prevention information
- Drug interactions with hormonal contraceptives
- Contraceptives in current use
- Guidelines for the follow-up of a reported pregnancy

Before trial enrollment, FOCBP must be advised of the importance of avoiding pregnancy during trial participation and the potential risk factors for an unintentional pregnancy. The subject and the subject's legally acceptable representative (eg, guardian) must sign an ICF/IAF stating that the above-mentioned risk factors and the consequences were discussed with them.

A urine pregnancy test for human chorionic gonadotropin (hCG) will be performed at screening on all female subjects ≥ 12 years of age and all female subjects < 12 years of age, if menstruation has started. If a urine test is performed and is positive, the investigator will follow-up with a confirmatory serum test.

During the trial, all FOCBP should be instructed to contact the investigator immediately if they suspect they might be pregnant (eg, missed or late menstrual cycle).

If a subject is suspected to be pregnant before she receives IMP, the IMP administration must be withheld until the results of serum pregnancy tests are available. If the pregnancy is confirmed, the subject must not receive the IMP and must not be enrolled in the trial. If pregnancy is suspected while the subject is taking IMP, the IMP must be withheld immediately (if reasonable, taking into consideration any potential withdrawal risks) until the result of the pregnancy test is known. If pregnancy is confirmed, the IMP will be permanently discontinued in an appropriate manner (eg, dose tapering if necessary for subject safety) and the subject will be withdrawn from the trial. Exceptions to trial

Protocol 31-14-204

discontinuation may be considered for life-threatening conditions only after consultations with the Clinical Safety and Pharmacovigilance department (see the cover page of this protocol for contact information).

The investigator must immediately notify the sponsor of any pregnancy associated with IMP exposure during the trial and for 30 days after the last dose of IMP, and record the event on the IRE form and forward it to the sponsor. The sponsor will forward Pregnancy Surveillance Form(s) for monitoring the outcome of the pregnancy.

Protocol-required procedures for trial discontinuation and follow-up must be performed on the subject unless contraindicated by pregnancy (eg, x-ray studies). Other appropriate pregnancy follow-up procedures should be considered, if indicated. In addition, the investigator must report to the sponsor, on appropriate Pregnancy Surveillance Form(s), follow-up information regarding the course of the pregnancy, including perinatal and neonatal outcome. Infants will be followed for a minimum of 6 months from the date of birth.

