 - Mental retardation
 - Pervasive developmental disorder
 - Tardive dyskinesia
 - Traumatic brain injury
 - Stroke
 - Restless legs syndrome
- 2) The subject has a history of schizophrenia, bipolar disorder, or other psychotic disorder.
 - 3) Subjects who receive psychostimulants for the treatment of attention-deficit hyperactivity disorder (ADHD) and who have developed and/or had exacerbations of the tic disorder after the initiation of stimulant treatment. (Note that subjects with ADHD who are treated with psychostimulants and have not developed new tics or a worsening of their current tics can be included if all other enrollment obligations are met).
 - 4) The subject currently has a primary diagnosis that meets DSM-5 criteria for mood disorder.
 - 5) The subject has severe obsessive-compulsive disease, as evidenced by a Children's Yale-Brown Obsessive Compulsive Scale (CY-BOCS) score > 16.
 - 6) The subject has taken aripiprazole within 1 month (30 days) of the screening visit.
 - 7) The subject has a history of neuroleptic malignant syndrome.
 - 8) Subject is a sexually active male or female of childbearing potential (FOCBP) (all female subjects \geq 12 years of age and all female subjects < 12 years of age if menstruation has started) who will not agree to practice 2 acceptable methods of birth control or who will not remain abstinent during the trial and for 30 or 90 days following the last dose of IMP for females and males, respectively. Abstinence will be permitted if it is confirmed and documented at every trial visit.

Protocol 31-14-204

- 9) The subject represents a significant risk of committing suicide based on history (suicide attempt in past 1 year), routine psychiatric status examination, investigator's judgment, or who has an answer of "yes" on any question other than 1-3 (current or over the last 30 days) on the baseline/screening version of the Columbia-Suicide Severity Rating Scale (C-SSRS).
- 10) The subject has a body weight < 16 kg.
- 11) Subjects who have taken neuroleptic or antiparkinson drugs within 14 days prior to baseline.
- 12) Subjects requiring cognitive-behavioral therapy (CBT) for TD during the trial period. CBT for other nonexclusionary disorders must remain consistent throughout the trial.
- 13) The subject has met DSM-5 criteria for any significant psychoactive substance use disorder within the past 3 months.

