5.7.2 Follow-up of Serious Adverse Events and Immediately Reportable Events

This trial requires that subjects be actively monitored for SAEs up to 30 (+ 3) days after the last dose of IMP is administered.

Serious AEs and nonserious IREs that are **identified or ongoing at the last scheduled contact** must be recorded as such on the AE eSource page. If updated information (eg, resolved status) on SAE or IRE status becomes available after a subject's last scheduled contact (up to last in-clinic visit for the entire trial), this must be reported to the sponsor and recorded on the AE eSource, according to the appropriate reporting procedures. The investigator will follow SAEs until the events are resolved, stabilized, or the subject is lost to follow-up or has died. Resolution means that the subject has returned to the baseline state of health and stabilized means that the investigator does not expect any further improvement or worsening of the subject's condition. The investigator will continue to report any significant follow-up information to the sponsor up to the point the event has resolved or stabilized, or the subject is lost to follow-up or has died.

5.7.3 Follow-up and Reporting of Serious Adverse Events and Immediately Reportable Events Occurring after Last Scheduled Contact

Any new SAEs reported to the investigator which occur **after the last scheduled contact** and are determined by the investigator to be reasonably associated with the use of the IMP, should be reported to the sponsor. This may include SAEs or IREs that are captured on follow-up telephone contact or at any other time point after the defined trial period. The investigator should follow SAEs or IREs identified after the defined trial period and continue to report any significant follow-up information to the sponsor until the events are resolved or stabilized, or the subject is lost to follow-up or has died.

Protocol 31-14-204

6 Pharmacokinetic Analysis

No PK analysis is planned.

7 Statistical Analysis

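### Section 5.5 sets a 30-day post-dose contraception period for sexually active males, 60 days shorter than the 90 days in exclusion criterion 8

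*Protocol*

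**What the plan says.** Exclusion criterion 8 appears twice in the current protocol, once among the key exclusion criteria in the synopsis and once in Table 3.4.3-1 (Section 3.4.3). Both versions exclude a sexually active male or a female of childbearing potential who will not use two accepted contraceptive methods or stay abstinent during the trial and "for 30 or 90 days following the last dose of IMP for females and males, respectively". The post-dose period is therefore 30 days for females and 90 days for males.

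Section 5.5 (Pregnancy) states the requirement again as an instruction to sites. It begins "For FOCBP and for males who are sexually active, there must be a documented agreement", and the agreement is that the subject or partner will take effective measures "to prevent pregnancy during the course of the trial and for 30 days after the last dose of IMP". It gives no separate period for males.

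Later in Section 5.5 the investigator is told to notify the sponsor of "any pregnancy associated with IMP exposure during the trial and for 30 days after the last dose of IMP".

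**The concern.** Section 5.5 tells the site what agreement to document, and criterion 8 decides whether the subject may enter. If the two give different periods for the same boy, a site can comply with one and fall short of the other.

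Three things are at stake:

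- **The instruction to subjects.** A sexually active adolescent male could be told 30 days at one site and 90 at another.
- **The eligibility record.** A 30-day agreement does not show that criterion 8 was satisfied. Section 3.13 counts enrolment in breach of the eligibility criteria among its examples of significant deviations, so following Section 5.5 to the letter can raise a deviation question.
- **No later correction.** Under Section 3.7.1.9 the only planned contact after treatment is a telephone call 30 (+3) days after the last trial visit. For days 31 to 90 a male subject has only what he was told and agreed to earlier.

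**Working it through.** This is a comparison of texts with one subtraction. No sample-size, power or alpha figure is involved.

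**Inputs**

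| Subjects | Criterion 8 (synopsis and Table 3.4.3-1) | Section 5.5 | Difference |
|---|---|---|---|
| Females of childbearing potential | 30 days | 30 days | 30 − 30 = 0 days |
| Sexually active males | 90 days | 30 days | 90 − 30 = 60 days |

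For males, the Section 5.5 agreement spans 30/90 = 33% of the criterion 8 period. Days 31 to 90 are missing from it. The 33% compares two stated durations; it does not measure exposure or risk.

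**Can any reading remove the difference?**

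1. *Section 5.5 applies to females only.* No. Its sentence names sexually active males.
2. *The 90 days in criterion 8 does not belong to males.* No. The wording assigns the two periods to females and males in that order.
3. *The 30 or 90 days in criterion 8 attaches only to abstinence.* This would leave its contraception option with no stated duration. It would also give males 90 days if abstinent but 30 if using contraception, which is not sensible.
4. *The two places state different rules.* No. Both require two methods, and both draw on the same list of methods in Table 3.4.3-1 and Section 5.5.
5. *One text is superseded.* No. All three statements are in the current body of the protocol, and none gives precedence to another.

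**Does it open a gap in pregnancy reporting?** Not on the text. Section 5.3 requires a report once site staff "become aware of any SAE, serious hepatotoxicity, or confirmed pregnancy", with no time limit. Section 5.7.3 allows for immediately reportable events captured "at any other time point after the defined trial period". The 30-day notification sentence in Section 5.5 therefore does not bar a later report.

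**The case against.** The strongest counter-argument is that both rules can be met at once. Agreeing to 90 days also satisfies a 30-day agreement, Section 5.5 does not call 30 days a maximum, and criterion 8 is the gate checked at screening and baseline. On that view the stricter rule still binds and the conflict is only a possible misreading. It is true that a careful site would document 90 days. But that relies on staff noticing a conflict the protocol does not flag, and the section that prescribes the agreement names males and gives them the shorter period.

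Other points on that side, and what remains of them:

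- **It is a wording inconsistency, not a design flaw.** Agreed. Nothing here shows which period is pharmacologically right, so the remedy can go either way.
- **What subjects sign is in the consent and assent forms, which were not available for review.** Agreed. They may already state 90 days for males, so the consent step is a check first and a change only if needed.
- **Days 31 to 90 are not monitored under either wording.** True. Contraception status is not recorded at the follow-up contact in Table 3.7-2. The effect is confined to the instruction given beforehand, which is the reason its stated duration should be right.
- **The SAP (Sections 8.1.1 and 14) records early termination.** This limits the practical value of an amendment now, but the contradiction is still in the text that governed sites.

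**Conclusion.** The concern holds. For sexually active males, Section 5.5 requires a documented post-dose agreement 60 days shorter than criterion 8 (30 against 90 days); for females there is no difference. As written, a site following Section 5.5 would document an agreement that does not meet the eligibility rule.

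The scope is narrow. Only sexually active males are affected, and the documents do not say how many there would be in this population aged 6 to 17. The efficacy analysis is unaffected, and no gap in pregnancy reporting is shown. The conclusion rests on the protocol text alone and assumes nothing about the consent forms or about which period is clinically necessary. It is a safety-instruction error that should be corrected because it is clear and nearly free to fix.

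**What to change.** Amend the sentence in Section 5.5 so that the agreement runs for 30 days after the last dose for females of childbearing potential and 90 days for sexually active males, matching criterion 8. If the sponsor's safety team judges 30 days sufficient for males, change criterion 8 to 30 days in both the synopsis and Table 3.4.3-1 instead.

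Whichever period is chosen, check the consent and assent forms and align them if they differ. If pregnancies in partners of male subjects are meant to be covered, also match the 30-day notification sentence in Section 5.5 to the male period; otherwise leave it as it is.

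The cost of the main change is one sentence in Section 5.5, plus consent and assent wording if the check shows it is needed. Data collection, sample size and analysis stay the same.

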5.6 Procedure for Breaking the Blind

The investigator is encouraged to contact the sponsor/contract research organization (CRO) medical advisor to discuss their rationale for unblinding. However, to prevent delays to the investigator or medical personnel responding to a potentially emergency situation, unblinding of IMP will not be dependent upon the investigator receiving approval from the sponsor/CRO medical advisor (ie, the investigator will be able to obtain the code break information independent of the sponsor/CRO medical advisor). The investigator must contact the sponsor/CRO medical advisor by telephone or e-mail with an explanation of the need for opening the treatment assignment code within 24 hours of opening the code. If the blind is broken, the Clinical Safety and Pharmacovigilance department must be notified immediately (see the cover page of this protocol for contact information). Documentation of breaking the blind should be recorded in the subject's medical record with the date and time the blind was broken and the names of the personnel involved. Once the blind is broken for a subject, that subject may not reinitiate treatment with the IMP.

